11. Current diagnosis and/or treatment of active liver disease including abnormal baseline liver function tests as defined as: total bilirubin greater than or equal to 3.0mg/dL AND either AST greater than or equal to 135 IU/L OR ALT greater than or equal to 150 IU/L.
 12. On hemo or peritoneal dialysis or have a creatinine of ≥ 2.0 mg/dL or estimated CrCl ≤ 50 mL/min.
 13. History of hypokalemia defined as less than 3.5 mEq/L on more than one occasion during the 4 weeks prior to enrollment.
 14. History of cardiovascular disease with increased risk for torsades de pointes as defined as:
 - a. NYHA Heart Failure Criteria III or greater; OR
 - b. History of atrial or ventricular dysrhythmias; OR
 - c. History of structural heart disease (including previously repaired); OR
 - d. Personal or family history of congenital long QT syndrome.
 15. A marked baseline prolongation of the QT/QTc interval as defined as a QTc interval > 450 milliseconds (ms) for male subjects or > 470ms for female subjects with repeated demonstration*.

* Subjects without a history of prolonged QTc and an abnormal baseline QTc interval should undergo repeat ECG assessment within screening period prior to randomization (72 hours) to confirm prolongation. If the repeat ECG QTc is within normal limits and less than the parameters above, the subject may be considered for enrollment.
 16. Pregnant or lactating females.
 17. History of azole intolerance or allergy.
 18. Individuals for whom study participation would not be in their best interest, as determined by the clinical investigator.
 19. Are taking medications that are contraindicated with concurrent use of fluconazole (See Section 6.6.1: Contraindicated Medications).
 20. Positive point of care HIV test at Day 1 visit consistent with new HIV diagnosis.

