7. STUDY SCHEDULE

7.1. Pre-Screening Assessment [Optional] (occurring up to 72 hours prior to enrollment)

NOTE: For situations in which performance of safety laboratory assessments in advance of screening visit allow for greater feasibility. For patients referred to study with existing standard of care safety labs, physical exam, and/or ECG within the past 72 hours and are available to the study team at the time of screening, these SOC activities can serve as the screening activities and do not require repeating. (Safety laboratory tests are required to have the same normal range values as the primary study site).

The following activities will be performed:

- Provide potential subjects with an abbreviated description of this trial and ask them to read and sign the pre-screening informed consent form. The pre-screening informed consent form will be signed prior to performing any screening procedures.
- Perform an HIV antibody test (point of care (POC) or local clinical laboratory)
- Collect approximately 10 mL of venous blood for Hepatic function panel (AST, ALT, Alkaline phosphatase and total bilirubin), BUN, Creatinine.
- Record a resting (5-minute rest period) 12-lead ECG.
- Notify the potential subject that they will receive a telephone call with the results of the safety laboratory testing (including: AST, ALT, Alkaline phosphatase and total bilirubin, BUN and creatinine) and ECG results to review and explain test results and whether they are eligible to participate in the study. Subjects without a history of prolonged QTc, whose baseline ECG shows prolonged QTc interval may be asked to return for repeat 12-lead ECG prior to determination of eligibility status. Eligible subjects will be asked to return for enrollment visit with the study team.

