 - Collect approximately 10 mL of venous blood for Hepatic function panel (AST, ALT, Alkaline phosphatase and total bilirubin), BUN, Creatinine. (will not need to be repeated if completed as part of pre-screening assessment)
 - Collect approximately 15 mL of venous blood for Coccidioidal serologies (CF; qualitative IDCF and IDTP; EIA-IgM; EIA IgG; and quantitative IDCF)
 - In addition the subject will be allowed the option to consent for additional sample collection (urine specimen, blood specimen [20 mL], nasopharyngeal swab, and throat swab) to be banked and used in future studies
 - The investigator will inform the subject of the results of the POC HIV -1 antibody test and provide counseling as to the meaning of the results, whether positive or negative. If the POC HIV-1 antibody test is positive and the participant does not have a prior diagnosis of HIV infection, the subject will no longer be considered eligible for participation in the study and the study product should not be administered. Counseling regarding the preliminary result and the need for a confirmatory test should be done by the site research team. A positive confirmatory test for those patients with a positive POC HIV testing will require counseling about the results and a recommendation to follow-up for care. Newly diagnosed HIV infections will receive additional counseling concerning the significance and possible risks to other people. Individuals with newly diagnosed HIV infections will be referred to the subjects clinical care provider and any other appropriate local resource. All test results, positive or negative, will be kept confidential to the extent permissible under the law. All positive results will be reported to the state's Division of Public Health as required by law. All confirmatory testing will be done following the institution's policy or the standard of care.
 - The investigator must review all safety laboratory results (including: AST, ALT, Alkaline phosphatase and total bilirubin, BUN, and creatinine), ECG results for QT prolongation, pregnancy test results, POC HIV test and eligibility criteria before the subject is randomized. Subjects who do not qualify for the study based on the results of the screening procedures

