should not be randomized. Subjects whose baseline ECG shows prolonged QTc interval may be asked to return for repeat 12-lead ECG prior to determination of eligibility status. Counseling regarding POC HIV testing and risk of false positives should occur by the site research team prior to the test being done.

- Enroll subjects in AdvantageEDC.
- Dispense the next available treatment assignment in sequence of study product (fluconazole or placebo) available at the site. Regardless of time the product is dispensed, observe subject taking 2 capsules (at once) in the clinic, and instruct subject to select a time of day to take their daily dose. If dosing cannot occur within 72 hours of the discharge from the facility where antibacterials for CAP were prescribed, then the subject should not be dosed and study activity must cease. Ideally, pills should be taken at the same time each day. Instruct subjects to bring their pill bottles to each visit. Review with subject that the study product should be stored at room temperature. Dispense 2 study product bottles (bottle A and B).
- Instruct subjects to notify the study center if they develop any severe reactions after study product dosing. If the site principal investigator or appropriate sub-investigator deems the reaction severe enough, further instructions will be given to the subject on the proper course of action, including a return to the clinic for immediate evaluation if appropriate.

Documentation of the subject's fulfillment of the entry criteria, for all subjects considered for the study and subsequently included or excluded, is to be completed. Documentation of screening failure details may be recorded using eligibility screening forms or a subject screen failure log. Screen failures will be entered in AdvantageEDC.

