8.2. Laboratory Evaluations

8.2.1. Clinical Laboratory Evaluations

Clinical screening laboratory parameters to be evaluated on Day 1 (or at pre-screening visit) to confirm study eligibility prior to receipt of the first study drug and will include a hepatic function panel (AST, ALT, Alkaline phosphatase, and total bilirubin), BUN, creatinine and HIV-1 POC testing. A urine or serum pregnancy test will be performed in women of child-bearing potential. To be eligible for participation in this trial the subject's clinical screening laboratory evaluations must be confirmed to meet the eligibility criteria as outlined in the Subject Eligibility Criteria.

- The hepatic panel (AST, ALT, Alkaline phosphatase, and total bilirubin), BUN, creatinine and POC HIV-1 testing will be performed by the local or site laboratory with same day resulting. A venous blood sample (approximately 10 mL) will be collected from each subject at the Day 1 or pre-screening visit. Safety labs completed as part of standard of care within the past 72 hours and that are available to the study team at the time of screening can serve as the screening activities and do not require repeating. (Laboratory screening tests are required to have the same normal range values as the primary study site).
- The urine or serum pregnancy test will be performed in women of child-bearing potential will be performed by the local or site laboratory with same day resulting. No additional sample will be needed if a serum test is desired.

Clinical safety laboratory parameters to be evaluated on Days 22, 29 and 43 include hepatic function panel (AST, ALT, Alkaline phosphatase, and total bilirubin), BUN, creatinine and pregnancy test (urine or serum) for women of child-bearing potential. These evaluations will be performed by the local or site laboratory with same day resulting. Venous blood samples (approximately 10 mL) will be collected from each subject on specified study days.

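### Exclusion 13 sets a potassium limit but can be applied only from values already on record, because the entry chemistry does not measure potassium; adding it would be a cheap safety improvement

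*Combined protocol and SAP*

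**What the plan says.** Criterion 13 (Section 5.2) excludes on "History of hypokalemia defined as less than 3.5 mEq/L on more than one occasion during the 4 weeks prior to enrollment". At least two low values within four weeks are therefore needed.

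Section 8.2.1 gives the purpose of the entry tests: "Clinical screening laboratory parameters to be evaluated on Day 1 (or at pre-screening visit) to confirm study eligibility". It gives their content as tests that "will include a hepatic function panel (AST, ALT, Alkaline phosphatase, and total bilirubin), BUN, creatinine and HIV-1 POC testing". Section 7.2 repeats the chemistry for Day 1: "Collect approximately 10 mL of venous blood for Hepatic function panel (AST, ALT, Alkaline phosphatase and total bilirubin), BUN, Creatinine". Section 7.1 (pre-screening) and the safety-laboratory footnote to Table 12 list the same analytes. Before randomisation the investigator must review these results together with "ECG results for QT prolongation, pregnancy test results, POC HIV test and eligibility criteria before the subject is randomized".

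The protocol also says where history comes from. Inclusion criterion 6 requires that records be available to the study team, Section 7.2 calls for a record review for eligibility, and Section 8.1 takes the medical history from the record and from interview. Safety laboratory results from routine care in the past 72 hours are accepted in place of study tests: "these SOC activities can serve as the screening activities and do not require repeating".

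**The concern.** The trial has a numeric potassium limit but no study procedure that produces a potassium value. The record review can find only what routine care happened to measure. A patient whose potassium was never tested cannot meet criterion 13, and so passes it.

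This matters because of the protocol's own reasoning. Section 2.3.1 names electrolyte abnormalities among the circumstances in which fluconazole has been linked to torsades de pointes. It also describes macrolide- or fluoroquinolone-based treatment as first-line outpatient care for this pneumonia. Section 6.6.1 allows erythromycin or clarithromycin if prescribed within the past 72 hours. A patient with an unmeasured low potassium and a baseline QTc within limits can therefore start 42 days of fluconazole alongside a QT-active antibacterial, without anyone in the trial knowing the potassium.

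**Working it through.** There is no stated figure to reproduce; the check is a comparison of texts.

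**Step 1. Is potassium in any listing of the entry chemistry?**

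| Place | Chemistry listed | Potassium |
|---|---|---|
| Section 7.1, pre-screening | AST, ALT, alkaline phosphatase, bilirubin, BUN, creatinine | no |
| Section 7.2, Day 1 draw and pre-randomisation review | same six | no |
| Section 8.2.1 | same six | no |
| Table 12 footnote | same six | no |

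Result: 0 of 4 listings.

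**Step 2. Which chemistry limits in criteria 11 to 13 are measured at entry?**

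| Analyte | Limit | Measured at entry |
|---|---|---|
| Total bilirubin | 3.0 mg/dL (criterion 11) | yes |
| AST | 135 IU/L (criterion 11) | yes |
| ALT | 150 IU/L (criterion 11) | yes |
| Creatinine | 2.0 mg/dL, also used for clearance (criterion 12) | yes |
| Potassium | 3.5 mEq/L (criterion 13) | no |

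Result: 4 of 5. Two qualifications apply. Criteria 11 and 12 concern current status, whereas criterion 13 concerns history. The HIV RNA and CD4 limits in criterion 10 also rest on records, though only for patients with known HIV infection.

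**Step 3. Who passes criterion 13 as written?**

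- No potassium on record: passes, with the current value unknown.
- One low value on record: passes, because the rule asks for more than one.
- Two or more low values within four weeks: excluded.

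The second outcome is the sponsor's stated threshold at work. The gap is the first.

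**Step 4. Does another safeguard supply the value?** Criterion 14 (cardiac history), criterion 15 (baseline QTc), criterion 18 (investigator judgement) and criterion 19 (contraindicated drugs) all reduce the risk. So do the eligibility reviews at Days 22 and 29. The individual stopping rules (Sections 5.3.3.1 and 9.2.3) and halting rule B (Section 9.5: more than 1% and at least 2 randomised subjects) act after an event. None of these requires a potassium result.

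**Step 5. Illustration of size.** The documents give neither the prevalence of hypokalaemia nor the share of patients with a recent potassium result. Assume, with no source in the documents, that 1% to 5% of patients have a low value that criterion 13 misses:

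- 0.01 × 1,000 = 10 and 0.05 × 1,000 = 50 patients
- at 1:1 allocation, an expected 5 to 25 on fluconazole

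These are counts of low values, not of arrhythmias.

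**The case against.** The strongest reply is that nothing here is inconsistent. Criterion 13 asks about history over four weeks, a history is read from records, and the protocol requires those records and their review. One Day 1 potassium could not by itself show more than one low value. This stands. A reader might infer that the protocol contradicts itself or that the criterion cannot be applied; the text supports neither reading.

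A second reply is that the sponsor chose repeated low values as the threshold. Section 2.3.1 lists its grounds for excluding patients at high risk of torsades (baseline QTc, cardiac disease, anti-arrhythmic drugs, family history), and potassium is not among them. The same passage names female sex as a risk factor, yet women are enrolled, so naming a risk factor does not in itself require a screening test. This also stands. A reader might infer that a single low potassium should exclude a patient. That would be a new exclusion, and the documents do not call for it.

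Third, the risk is managed through the QT interval itself, with an ECG before randomisation. This is real but partial mitigation: a QTc within limits at entry does not reveal the potassium of someone about to start the drug. Section 8.1 schedules no further ECG except at early termination, and Section 7.4.1 restricts that to termination before Day 15.

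Fourth, the harm is not quantified. The QTc change in up to 20% of patients cited in Section 2.3.1 comes from a haematologic malignancy cohort, while criterion 8 excludes patients on anti-neoplastic chemotherapy. That figure should not be carried over to this trial.

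**Conclusion.** The point holds as a cheap improvement in patient safety, between optional and recommended. Confidence is high that potassium is absent from all four listings and that criterion 13 therefore depends on what the record already contains. How many patients this affects is unknown: 10 to 50 per 1,000 rests wholly on the assumed 1% to 5%, and no event rate can be attached to it. Sample size, power and type I error are not affected.

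The conclusion is limited to entry. It does not show that patients will be harmed or that the threshold in criterion 13 is wrong. Whether potassium or ECG should be monitored during treatment is a separate question.

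**What to change.** 1. Add potassium to the chemistry in Sections 7.1, 7.2 and 8.2.1, and to the Table 12 footnote marked as Day 1 only, since that footnote covers every visit.
2. Accept a routine-care potassium from the past 72 hours on the same terms as the other safety tests.
3. Add potassium to the results that Section 7.2 requires the investigator to review before randomisation.
4. Keep the criterion 13 threshold and state that the screening value counts as one occasion. A routine-care value used as the screening value counts once, not twice.
5. Repeat a low screening value before dosing where feasible. Criterion 15 has a precedent for the ECG: patients with a first abnormal QTc "should undergo repeat ECG assessment within screening period prior to randomization (72 hours) to confirm prolongation". If no repeat is possible, the investigator judges under criterion 18.

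The outcomes follow without conflict. With no earlier low value, a normal screening value leaves the patient eligible. A low value with a normal repeat is one occasion, so criterion 13 does not exclude. A low value with a low repeat is two, so it does. One earlier low value plus a low screening value is also two, whatever the repeat shows.

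The cost is one more analyte, usually on the 10 mL already drawn. Patients whose routine-care results lack potassium would need an extra tube. The laboratory should confirm same-day reporting, which Section 8.2.1 states only for the tests it lists. Retests must fit the existing limit, since Section 7.2 stops study activity "If dosing cannot occur within 72 hours of the discharge from the facility where antibacterials for CAP were prescribed". Under the assumed 1% to 5%, that means 10 to 50 retests per 1,000 otherwise eligible patients. If every such patient were lost, 1,000/0.99 − 1,000 = 10.1 and 1,000/0.95 − 1,000 = 52.6, so at most 11 to 53 more otherwise eligible patients would be needed to enrol 1,000.

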5.3. Treatment Assignment Procedures

5.3.1. Randomization Procedures

Per International Conference on Harmonisation (ICH) guideline E6: Good Clinical Practice (GCP), screening records will be kept at each participating site to document the reason why an individual was screened, but failed trial entry criteria. The reasons why individuals failed

screening will be recorded in the Statistical and Data Coordinating Center's (SDCC) AdvantageEDCSM (Electronic Data Capture System).

Using a centralized randomization system, eligible subjects will be randomly assigned to 1 of 2 groups (1:1 ratio) to receive either 42 days of placebo or 400 mg/day fluconazole capsules. The randomization code will be prepared by statisticians at the SDCC and sent to the DMID Clinical Agents Repository where the study product will be labeled with a randomization code which links to the treatment assignment. Once consented and determined to be eligible for the trial, the subject will be assigned the next available assignment in sequence of the product available at the site. The randomization code of the distributed study product will be entered into AdvantageEDC upon enrolling the subject in the trial. Instructions for use of the enrollment module are included in the AdvantageEDC User's Guide.

If emergency unblinding is required, the site may determine the treatment assignment by contacting the SDCC or through AdvantageEDC.

Subjects who sign the informed consent form and are randomized but do not ingest the study drug will be replaced. Subjects who sign the informed consent form, and are randomized, receive the study drug, and subsequently withdraw consent, are withdrawn or terminated from the study, or are lost to follow-up will not be replaced.

5.3.2. Masking Procedures

This is a double-blind, randomized clinical trial.

Subjects, investigators, study personnel performing any study-related assessments following study drug administration, and laboratory personnel performing antibody assays will be blinded to group assignment until all study assessments through the Day 43 visit are completed.

The randomization scheme will be generated by the SDCC. In case of a need for emergency unblinding, in order to disclose the assignment to the subject health care providers, the site may determine the treatment assignment through AdvantageEDC or by contacting the SDCC. The site will notify DMID and the appropriate IRB(s) immediately in the event of emergency unblinding. Refer to Section 6.7 for criteria for removing subjects from treatment and initiation of rescue procedures.

On Day 43, subjects will be informed of their treatment assignment and results of serologic testing from Days 1, 22, and 29. For the remainder of the study, subjects will know if they met the primary case definition of CAP caused by acute coccidioidomycosis infection. See the appropriate section of the Manual of Procedures for the appropriate sequence of events prior to informing the subjects if they met the protocol defined case definition of CAP caused by acute coccidioidomycosis infection.

Subjects who withdraw or are terminated from the study will be provided their treatment assignment. When available, the subject will be informed if the subject met the protocol defined

case definition of CAP caused by acute coccidioidomycosis. In addition, subjects will be provided with all available Coccidioidal serologies results.

5.3.3. Reasons for Withdrawal and Discontinuation of Study Product Administration

Subjects may voluntarily withdraw their consent for study participation at any time and for any reason, without penalty. Subjects may also withdraw voluntarily from receiving the study intervention for any reason. An investigator may also withdraw a subject from receiving the study intervention for any reason. If a subject withdraws or is withdrawn prior to completion of the study, the reason for this decision must be recorded in the case report forms (CRFs). Follow-up safety evaluations will be conducted, if the subject agrees.

5.3.3.1. Discontinuation from Treatment

In addition, a subject will be discontinued from the active treatment and continue to be followed if the subject meets any of the following reasons:

- If any of the following criteria for liver-related adverse events are met and confirmed:
 - AST elevation of >5X ULN or greater than or equal to 225 IU/L or
 - ALT elevation of >5X ULN or greater than or equal to 250 IU/L or
 - Total bilirubin elevation >1.5X ULN or
 - Aminotransferase elevation of >3X ULN accompanied by total bilirubin elevation >1.5X ULN
- If any subject experiences any of the following:
 - QTc prolongation as defined by a corrected QT of > 500ms OR > 60ms above baseline measurement
 - Torsades de pointes (torsades, TdP)
 - Unexplained Syncope
 - Seizure in non-epileptic patients
- Medical disease or condition, or any new clinical findings that meet an exclusion criterion or for which continued participation, in the opinion of the site principal investigator or appropriate sub-investigator, would compromise the safety of the subject, would interfere with the subject's successful completion of the study, or would interfere with the evaluation of responses.
- A SAE as defined in the protocol. The subject will be followed until the resolution of the event.

-
- Pregnancy. The subject will be followed up to two months after delivery.
 - New information becomes available that makes further participation unsafe or no longer in the best interest of the subject.
 - Diagnosis of disseminated coccidioidomycosis.
 - Subsequent hospitalization for this CAP episode occurring greater than 72 hours after study randomization.
 - Worsening oxygenation: need for assisted ventilation including continuous positive airway pressure (CPAP), bilevel positive airway pressure (BIPAP), or mechanical ventilation.
 - Unable to adhere to scheduled study visits (e.g. relocation at a distance from the study center that precludes adherence)
 - Determined by a physician's discretion to require additional therapy not indicated in the protocol to ensure his/her health and well-being.

